5.1.5 Medical/Ethical

- Written informed consent in accordance with federal, local, and institutional guidelines.
- Females of childbearing potential (FCBP) must agree to ongoing pregnancy testing and to practice contraception. Should a woman become pregnant or suspect she is pregnant while she or her partner is participating in this study, she should inform her treating physician immediately.
- Male subjects must agree to practice contraception.
- No known hypersensitivity to murine products.
- Patients must have normal baseline cardiac function based upon echocardiogram or gated blood pool scan (MUGA) with an ejection fraction $\geq 50\%$.
- Patients who test positive for Hepatitis C Antibody are eligible provided all of the following criteria are met: a) bilirubin $\leq 2 \times$ upper limit of normal; b) ALT/AST $\leq 3 \times$ upper limit of normal; and c) clinical evaluation to rule out cirrhosis.
- Specific guidelines will be follow regarding inclusion of relapsed/refractory DLBCL based on Hepatitis B serological testing as follow:
 - HBsAg negative, HBcAb negative, HBsAb positive patients are eligible.
 - Patients who test positive for HBsAg are ineligible (regardless of other Hepatitis B serologies).
 - Patients with HBsAg negative, but HBcAb positive (regardless of HBsAb status) should have a HBV DNA testing done and protocol eligibility determined as follow:
 - If HBV DNA is positive, the subject will be excluded from the study.

- If HBV DNA is negative, the subject may be included but must undergo at least every 2 months HBV DNA PCR testing from the start of treatment throughout the duration the treatment course.

5.2. Inclusion of Women and Minorities

Both men and women and members of all races and ethnic groups are eligible for this study.

5.3. Exclusion Criteria

Subjects will be excluded from this study for the following:

- Patients with NHL other than DLBCL; including “transformed” DLBCL.
- Known to be seropositive for HIV. An HIV test is not required for entry on this protocol, but is required if the patient is perceived to be at risk.
- Positive serology for HBV defined as a positive test for HBsAg. In addition, if negative for HBsAg but HBcAb positive (regardless of HBsAb status), a HepB DNA test will be performed and if positive the subject will be excluded.
- Patients with symptomatic brain involvement.
- Peripheral neuropathy of Grade 2 or greater severity as defined by the National Cancer Institute’s (NCI) Common Terminology Criteria for Adverse Events (CTCAE) Version 4.0. Patients with Grade 2 or higher (NCI-CTC) neuropathy.
- Myocardial infarct within 6 months before enrollment, New York Heart Association (NYHA) Class II or greater heart failure, uncontrolled angina, severe uncontrolled ventricular arrhythmias, clinically significant pericardial disease, or electrocardiographic evidence of acute ischemia.
- Uncontrolled intercurrent illness including, but not limited to, active infection, poorly controlled hypertension, diabetes mellitus or other serious medical or psychiatric conditions that could interfere with adherence to or completion of this study.
- Pregnant or breastfeeding.
- Patient has received other investigational drugs within 4 weeks before enrollment.
- Chemotherapy within 3 weeks of the first scheduled study treatment.
- Less than 2-year disease free from another primary malignancy (other than squamous or basal cell carcinoma of the skin, “in-situ” carcinoma of the cervix or breast, superficial bladder carcinoma, or previously treated localized prostate cancer with normal PSA levels). Patients are not considered to have a “currently active” malignancy if they have completed anti-cancer therapy, are considered by their physician to be at less than 30% risk of relapse and at least 2 years have lapsed.
- Major surgery, other than diagnostic surgery, within 2 weeks.

- Known history of allergy to Captisol® (a cyclodextrin derivative used to solubilize carfilzomib).
- Medical condition requiring chronic use of high dose systemic corticosteroids (i.e., doses of prednisone higher than 10 mg/day or equivalent).
- Prior HDC-ASCT.
- Active CNS disease defined as symptomatic meningeal lymphoma or known CNS parenchymal lymphoma. A lumbar puncture demonstrating DLBCL at the time of registration to this study is not exclusion for study enrollment.

6. DRUG INFORMATION

6.1. Carfilzomib (Investigational Agent)

Generic Name: Carfilzomib is the generic name; formerly referred to as PR-171.

Chemical Name: (2S)-N-((S)-1-((S)-4-methyl-1-((R)-2-methyloxiran-2-yl)-1-oxopentan-2-ylcarbamoyl)-2-phenylethyl)-2-((S)-2-(2-morpholinoacetamido)-4-phenylbutanamido)-4-methylpentanamide.

Molecular Formula: C40H57N5O7

Molecular Weight: 719.9

Amgen, Inc. will supply non-commercial carfilzomib to the investigator. Carfilzomib for injection (formerly referred to as PR-171 for injection) is supplied as a lyophilized parenteral drug product in 45 mg and 60 mg single-use vials. Prior to administration, the lyophilized product is aseptically reconstituted with sterile water for injection. Upon reconstitution, carfilzomib for injection consists of 2 mg/mL carfilzomib, 100 mg/mL sulfob tylether beta-cyclodextrin (SBE- β -CD), and 1.9 mg/mL citrate buffer (pH 3 to 4).

Preparation: Remove the vial from the refrigerator just prior to use. Aseptically reconstitute each vial by slowly injecting 29 mL of sterile water for injection, directing the solution onto the inside wall of the vial to minimize foaming. Gently swirl and/or invert the vial slowly for about 1 minute, or until complete dissolution of any cake or powder occurs. Do not shake to avoid foam generation. If foaming occurs, allow the solution to rest in the vial for about 2 to 5 minutes, until foaming subsides. The reconstituted solution contains carfilzomib 2 mg/mL. After reconstitution, carfilzomib is ready for IV administration. When administering in an IV bag, withdraw the calculated dose from the vial and dilute into dextrose 5% injection 50 mL D5W bag. The reconstituted product should be a clear, colorless solution. If any discoloration or particulate matter is observed, do not use the reconstituted product.

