4.2. Target Accrual and Study Duration

A maximum of 21 patients for Phase I and 9 patients for the Phase Ib expansion part of this trial will be enrolled at Roswell Park and Network Sites (For Phase Ib only). The number of subjects required is a function of a currently unknown dose-toxicity relationship. Accrual is expected to take up to 10 years.

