6.1.2. Drug Preparation and Administration

Carfilzomib for injection is supplied as a lyophilized parenteral product in single-use vials. The lyophilized product is reconstituted with water for injection to a final carfilzomib concentration of 2 mg/mL prior to administration. The dose will be calculated using the subject's actual BSA at baseline. Subjects with a BSA > 2.2 m² will receive a dose based upon a 2.2 m² BSA.

IV hydration will be given immediately prior to carfilzomib during Cycle 1. This will consist of 250 mL to 500 mL normal saline or other appropriate IV fluid. If lactate dehydrogenase (LDH) or uric acid is elevated (and/or in subjects considered still at risk for TLS) at Cycle 2 Day 1, then the recommended IV hydration should be given additionally before each dose in Cycle 2. The goal of the hydration program is to maintain robust urine output (e.g., \geq 2 L/day). Subjects should be monitored periodically during this period for evidence of fluid overload.

If the subject has a dedicated line for carfilzomib administration, the line must be flushed with a minimum of 20 mL of normal saline prior to and after drug administration.

Carfilzomib will be given as an IV infusion over approximately 10 minutes. For doses > 27 mg/m², carfilzomib should be infused over 30 minutes. The dose will be administered at a facility capable of managing hypersensitivity reactions. Subjects will remain at the clinic under observation for at least 1 hour following each dose of carfilzomib in Cycle 1 and following the dose on Cycle 2 Day 1. During these observation times, post dose IV hydration (between 250 mL and 500 mL normal saline or other appropriate IV fluid formulation) will be given. Subjects should be monitored periodically during this period for evidence of fluid overload.

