6.1.3. Storage and Stability

Carfilzomib for injection is stored refrigerated at 2°C to 8°C. After addition of the appropriate amount of water for injection and vigorous mixing, the solution is administered as an IV infusion. Please note: the use of closed-system drug-transfer devices, where multiple stopper punctures in close proximity to one another can occur, is not recommended as it could result in clogging.

The reconstituted solution in its original vial can be stored in a refrigerator controlled at 2°C to 8°C (recommended), or at room temperature (15°C to 30°C) until use; and the reconstituted solution should not be frozen. Reconstituted carfilzomib for injection is a clear, colorless to slightly yellow solution, and is essentially free of visible particulates.

Parenteral drug products should be visually inspected for particulate matter and discoloration prior to administration, whenever solution and container permit. If particulate matter or discoloration is observed, the reconstituted product should not be used.

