- 3 Prior to study, at time of restaging; between Cycle 2 Day 15 to Cycle 2 Day 28 following Cycle 3 but before ASCT and at the end of treatment evaluation, then every 4 months (\pm 2 weeks) for 1 year, then every 6 months (\pm 2 weeks) for 2 years, then once a year (\pm 2 weeks) for 2 years for a total of 5 years, then as clinically indicated. The follow up period will begin at the end of study evaluation visit for patients that became ineligible for transplant for any reason but did not meet criteria for disease progression. The follow up period for patients that go on to transplant will begin at the Day +100 bone marrow biopsy.
- 4 At least every 4 months (\pm 1 week) for 1 year, then every 6 months (\pm 1 week) for 2 years, then once a year (\pm 2 weeks) for 2 years for a total of 5 years from study entry, then as clinically indicated. The follow up period will start at the Day 100 bone marrow biopsy in patients that received a transplant. Patients that progress will be followed for survival status only on a yearly basis.
- 5 If there is a greater than 10% difference in weight from baseline, then recalculate the BSA prior to each treatment; otherwise the actual dose given does not need to change.
- 6 CT Scan to be completed within 28 days prior to enrollment
- 7 When clinically appropriate.
- 8 CBC with differential and platelet counts will be monitored 3 times per week in between cycles of C-R-ICE until count recovery.
- 9 Days 1, 2, 8, and 9
- 10 All patients must be screened for hepatitis B infection (HBsAg/HBcAb) before starting treatment. Patients tested positive for HBV surface antigen are ineligible. Patients tested HBsAg negative/HBcAb positive should have qualitative HBV DNA PCR testing. If HBV DNA is positive the subject is excluded. If HBV DNA is negative, subject may be included but must undergo at least every 2 months HBV DNA PCR

testing from the start of treatment throughout the duration the treatment course. Monitoring during the on treatment periods is required at least every 2 months and during follow-up at a minimum of every 2 - 3 months up to 6 months after the last dose. Prophylactic antiviral may be initiated at the discretion of the investigator.

- 11 All patients must be screened for HCV infection before starting treatment. Patients who test positive for HCV antibody (Ab) evaluation of LFT's and clinical evaluation to rule out cirrhosis.
- 12 To be completed within 7 days prior to enrollment.

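### Section 6.1 gives one water volume (29 mL) for both carfilzomib vial strengths; it yields the stated 2 mg/mL for the 60 mg vial but only about 1.51 to 1.55 mg/mL for the 45 mg vial

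*Combined protocol and SAP*

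**What the plan says.** Section 6.1 of the combined protocol and SAP describes the investigational drug as "supplied as a lyophilized parenteral drug product in 45 mg and 60 mg single-use vials". The preparation paragraph in the same section then gives a single direction: "Aseptically reconstitute each vial by slowly injecting 29 mL of sterile water for injection". It states the outcome without reference to vial size: "The reconstituted solution contains carfilzomib 2 mg/mL". For bag administration, staff are told to "withdraw the calculated dose from the vial and dilute into dextrose 5% injection 50 mL D5W bag", so the volume drawn depends on the concentration they believe the vial holds.

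Two later sections touch on the same step. Section 6.1.2 says the product is "reconstituted with water for injection to a final carfilzomib concentration of 2 mg/mL prior to administration", and Section 6.1.3 says only "After addition of the appropriate amount of water for injection". Neither gives a volume. In the text available for review, 29 mL is the only reconstitution volume for carfilzomib. Nothing restricts it to the 60 mg vial, and nothing mentions overfill.

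**The concern.** The two strengths, the single volume and the single concentration cannot all be right at labelled content: equal volumes of water added to 45 mg and 60 mg of drug cannot both give 2 mg/mL. The protocol makes the distinction elsewhere. For ifosfamide, also supplied in two vial sizes, Section 6.3 gives a separate volume for each.

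What is at stake is agreement between the carfilzomib dose recorded and the dose delivered. Phase Ib is meant to describe safety and response at the MTD (Sections 3.2 and 13.5). A 45 mg vial prepared exactly as written, then drawn on the stated 2 mg/mL, would deliver less than the record shows, and the preparation text contains no warning. Section 4.2 plans 9 Phase Ib patients, with network sites joining in that phase, so more than one pharmacy may rely on this paragraph.

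**Working it through.** **Inputs.** Vial contents 45 mg and 60 mg, water 29 mL, stated concentration 2 mg/mL: all from Section 6.1. Powder displacement and overfill are not given and are treated below as assumptions.

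**Formula.** Concentration = content / (water added + volume displaced by the powder).

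**1. Reproduce the plan's figure with the 60 mg vial.**
- No displacement: 60/29 = 2.07 mg/mL.
- Displacement that makes the figure exact: 60/2 − 29 = 1 mL, giving 60/30 = 2.00 mg/mL.

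The stated 2 mg/mL reproduces.

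**2. Apply the same instruction to the 45 mg vial at labelled content.**
- No displacement: 45/29 = 1.55 mg/mL, which is 22.4% below 2 mg/mL.
- Displacement scaled from the 60 mg vial (1 × 45/60 = 0.75 mL, assumed): 45/29.75 = 1.51 mg/mL, which is 24.4% below.
- Cross-check: 29 mL at 2 mg/mL would contain 58 mg, 13 mg more than the label.

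The stated 2 mg/mL does not reproduce.

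**3. Could overfill explain it?** The ranges below run from no displacement to 0.75 mL.
- 5% overfill (47.25 mg): 1.63 to 1.59 mg/mL, 18.5% to 20.6% low.
- 10% overfill (49.5 mg): 1.71 to 1.66 mg/mL, 14.7% to 16.8% low.
- Overfill needed to reach 2 mg/mL: 58/45 − 1 = 28.9%, or 59.5/45 − 1 = 32.2%.

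**4. Effect on a dose drawn by volume at an assumed 2 mg/mL, labelled content.**
- Whole dose from one 45 mg vial: 22.5 mL is recorded as 45 mg. Delivered: 22.5 × 45/29 = 34.9 mg, or 22.5 × 45/29.75 = 34.0 mg (22% to 24% low).
- Mixed dose, one full 60 mg vial (60 mg) plus 22.5 mL from a 45 mg vial: recorded 60 + 45 = 105 mg. Delivered: 60 + 34.9 = 94.9 mg, or 60 + 34.0 = 94.0 mg (about 10% low).

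**5. Volume that would be right for the 45 mg vial.** Final volume = 45/2 = 22.5 mL. Water to add = 22.5 mL with no displacement, or 22.5 − 0.75 = 21.75 mL with the assumed displacement; roughly 22 mL.

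**The case against.** The best reply is that the target concentration is stated more than once. Section 6.1 gives 2 mg/mL twice, Section 6.1.2 makes it the end point of reconstitution, and Section 6.1.3 speaks of a suitable amount of water rather than a fixed one. A pharmacist who works to the target will not use 29 mL for a 45 mg vial, and may notice that 29 mL at 2 mg/mL implies 58 mg. On this view the fault is one sentence not tied to a vial size. Much of this stands: the error is avoidable, and an underdose needs 45 mg vials in the supply, the 29 mL followed literally, the dose drawn at 2 mg/mL, and little overfill. It does not make the sentence correct. The only written volume is wrong for one of the two listed strengths, and the paragraph asserts that this volume gives 2 mg/mL.

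Two stronger readings are tempting, and the documents support neither.

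- A reader might infer that patients' doses are 22% to 24% low. That holds only for a dose drawn wholly from 45 mg vials prepared this way. Both strengths are listed, and the amount at Dose Level 6, the Phase Ib dose named in Section 4.1, is not in the text available (the schema figure is not shown), so the mix of vials is unknown.
- A reader might infer that Phase I patients were underdosed, so that the MTD, DLT or PK results are in doubt. Nothing shows that a 45 mg vial was received, let alone prepared with 29 mL.

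It is also fair to say that the point does not touch the hypotheses, sample size, endpoint or analysis. It concerns whether the dose analysed is the dose given.

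**Conclusion.** Wrong as written. Section 6.1 is internally inconsistent for the 45 mg vial: at labelled content its instruction gives about 1.51 to 1.55 mg/mL, 22% to 24% below the concentration it states. The lower concentration assumes 0.75 mL of powder displacement, the higher none. Overfill would narrow the gap, but only an unstated 29% to 32% would close it.

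The effect on a patient is conditional. The part of a dose drawn from such a vial would be short by 22% to 24%; the total shortfall depends on how much of the dose comes from 45 mg vials, for example about 10% for the mixed dose worked above. This is a correctable error in a preparation instruction, not evidence that any dose was wrong.

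**What to change.** In Section 6.1, limit the 29 mL instruction to the 60 mg vial. Add a line for the 45 mg vial directing the volume in the manufacturer's preparation instructions that gives 2 mg/mL: a final volume of 22.5 mL, so roughly 22 mL of water (21.75 to 22.5 mL on the displacement assumptions above), with the manufacturer's figure governing. If 45 mg vials are not supplied to this study, delete that strength instead.

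The cost is one line in the next amendment, with the IRB approval that Section 17.1 requires. There are no added patients, visits or procedures. The sponsor may choose to ask pharmacies whether any 45 mg vials were received, but nothing in the documents makes that check necessary.

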6.1.1. Drug Shipment

Carfilzomib will be provided by Amgen, Inc. The site will document the date of receipt and condition of the shipment. The investigational pharmacist or designee will retain drug-shipment records.

6.1.2. Drug Preparation and Administration

Carfilzomib for injection is supplied as a lyophilized parenteral product in single-use vials. The lyophilized product is reconstituted with water for injection to a final carfilzomib concentration of 2 mg/mL prior to administration. The dose will be calculated using the subject's actual BSA at baseline. Subjects with a BSA > 2.2 m² will receive a dose based upon a 2.2 m² BSA.

IV hydration will be given immediately prior to carfilzomib during Cycle 1. This will consist of 250 mL to 500 mL normal saline or other appropriate IV fluid. If lactate dehydrogenase (LDH) or uric acid is elevated (and/or in subjects considered still at risk for TLS) at Cycle 2 Day 1, then the recommended IV hydration should be given additionally before each dose in Cycle 2. The goal of the hydration program is to maintain robust urine output (e.g., \geq 2 L/day). Subjects should be monitored periodically during this period for evidence of fluid overload.

If the subject has a dedicated line for carfilzomib administration, the line must be flushed with a minimum of 20 mL of normal saline prior to and after drug administration.

Carfilzomib will be given as an IV infusion over approximately 10 minutes. For doses > 27 mg/m², carfilzomib should be infused over 30 minutes. The dose will be administered at a facility capable of managing hypersensitivity reactions. Subjects will remain at the clinic under observation for at least 1 hour following each dose of carfilzomib in Cycle 1 and following the dose on Cycle 2 Day 1. During these observation times, post dose IV hydration (between 250 mL and 500 mL normal saline or other appropriate IV fluid formulation) will be given. Subjects should be monitored periodically during this period for evidence of fluid overload.

6.1.3. Storage and Stability

Carfilzomib for injection is stored refrigerated at 2°C to 8°C. After addition of the appropriate amount of water for injection and vigorous mixing, the solution is administered as an IV infusion. Please note: the use of closed-system drug-transfer devices, where multiple stopper punctures in close proximity to one another can occur, is not recommended as it could result in clogging.

The reconstituted solution in its original vial can be stored in a refrigerator controlled at 2°C to 8°C (recommended), or at room temperature (15°C to 30°C) until use; and the reconstituted solution should not be frozen. Reconstituted carfilzomib for injection is a clear, colorless to slightly yellow solution, and is essentially free of visible particulates.

Parenteral drug products should be visually inspected for particulate matter and discoloration prior to administration, whenever solution and container permit. If particulate matter or discoloration is observed, the reconstituted product should not be used.

6.1.4. Handling and Disposal

The Investigator or designee will be responsible for dispensing and accounting for all investigational drug provided by Amgen, Inc., exercising accepted medical and pharmaceutical practices. Study drugs must be handled as cytotoxic agents and appropriate precautions taken per the institution's environmentally safe handling procedures. All investigational drugs will be dispensed in accordance with the Investigator's prescription or written order.

Records of product lot numbers and dates received will be entered on a product accountability form. It is the Investigator's responsibility to ensure that an accurate record of investigational drug issued and returned is maintained.

Used vials (excess drug) will be destroyed according to standard practices at the site after properly accounting for the dispensing. Partially used vials of study drug will not be re-used for other subjects. Expired product and/or unused vials will be inventoried by the study monitor.

Under no circumstances will the Investigator supply investigational drug to a third party or allow the investigational drug to be used in a manner other than as directed by this protocol.

6.2. Rituximab (Rituxan®)

Rituximab is a chimeric monoclonal antibody. Rituximab binds to the CD20 antigen expressed on benign and malignant B-cells and causes cell death by complement mediated lysis, induction of apoptosis and by antibody dependent cellular cytotoxicity (ADCC).

Formulation: Rituximab is a genetically engineered, chimeric, murine/human monoclonal antibody directed against the CD20 antigen found on the surface of normal and malignant pre-B and mature B cells. The antibody is an IgG1 κ immunoglobulin containing murine light-and heavy-chain variable region sequences and human constant region sequences. Rituximab is composed of two heavy chains of 451 amino acids and 2 light chains of 213 amino acids (based on cDNA analysis) and has an approximate molecular mass of 145 kD. Rituximab has a binding affinity for the CD20 antigen of approximately 8nM. Rituximab is supplied as 100 mg and 500 mg sterile, preservative-free, single-use vials.

Supplier: Commercially available and will not be provided for this study.

Preparation: DO NOT ADMINISTER AS AN INTRAVENOUS PUSH OR BOLUS. Do not infuse rituximab concomitantly with another IV solution or other IV medications. The appropriate dose is withdrawn and diluted to a final concentration of 1 - 4 mg/mL in either 0.9% sodium chloride or 5% dextrose solution. The solution is then stable at 2° to 8°C for 24 hours and at room temperature for an additional 12 hours.

Storage: Vials can be stored at 2°C to 8°C. They should be protected from sunlight.

Administration: The first infusion should be administered at an initial rate of 50 mg/hr. If hypersensitivity or infusion-related events do not occur, the rate may be increased by 50 mg/hr every 30 minutes up to a maximum of 400 mg/hr. Subsequent infusions may be started at 100 mg/hr and the rate increased by 100 mg/hr at every 30 minutes to a maximum of 400 mg/hr, as tolerated. Rituximab may also be infused per institutional guidelines at the discretion of the PI. Patients will be premedicated with acetaminophen 650-mg po and diphenhydramine 50 mg IV 30 minutes prior to beginning the rituximab infusion. For severe reactions, the infusion will be stopped and can be resumed at 50% of the prior rate once the reactions are treated and symptoms resolved.

Toxicity:

- **Common:** Fever, chills, fatigue, headache; less common: nausea, vomiting, rhinitis, pruritus, hypotension; rare: neutropenia, thrombocytopenia, asthenia, arthritis, vasculitis,

lupus-like syndrome, pleuritis, bronchiolitis obliterans, uveitis, optic neuritis, and skin reactions such as toxic epidermal necrolysis and pemphigus.

- **Fatal Infusion Reactions:** Severe and fatal cardiopulmonary events, including angioedema, hypoxia, pulmonary infiltrates, acute respiratory distress syndrome, myocardial infarction, and cardiogenic shock, have been reported. These severe reactions typically occurred during the first infusion with time to onset of 30 - 120 minutes.
- **Cardiac Events:** Patients with preexisting cardiac conditions, including arrhythmia and angina, have had recurrences of these cardiac events during rituximab infusions.
- **Tumor Lysis Syndrome (TLS):** TLS has been reported and is characterized in patients with a high number of circulating malignant cells ($\geq 25,000 \mu\text{L}$) by rapid reduction in tumor volume, renal insufficiency, hyperkalemia, hypocalcemia, hyperuricemia, and hyperphosphatemia.
- **Renal Events:** Rituximab has been associated with severe renal toxicity including acute renal failure requiring dialysis, and in some cases has led to death. Renal toxicity has occurred in patients with high numbers of circulating malignant cells ($\geq 25,000/\text{mm}^2$) or high tumor burden who experience tumor lysis syndrome and in patients administered concomitant cisplatin.
- **Mucocutaneous Reactions:** Severe bullous skin reactions, including fatal cases of toxic epidermal necrolysis and paraneoplastic pemphigus, have been reported in patients treated with rituximab. The onset of reaction has varied from 1 to 13 weeks following rituximab exposure.
- **Hematologic Events:** In clinical trials, Grade 3 and Grade 4 cytopenias were reported in 48% of patients treated with RITUXIMAB; these include: lymphopenia (40%), neutropenia (6%), leukopenia (4%), anemia (3%), and thrombocytopenia (2%). The median duration of lymphopenia was 14 days (range, 1 to 588 days) and of neutropenia was 13 days (range, 2 to 116 days). A single occurrence of transient aplastic anemia (pure red cell aplasia) and two occurrences of hemolytic anemia following RITUXIMAB therapy were reported.

In addition, there have been a limited number of post-marketing reports of prolonged pancytopenia, marrow hypoplasia, and late onset neutropenia (defined as occurring 40 days after the last dose of RITUXIMAB) in patients with hematologic malignancies. In reported cases of late onset neutropenia (NCI-CTC Grade 3 and Grade 4), the median duration of neutropenia was 10 days (range 3 to 148 days). Documented resolution of the neutropenia was described in approximately one-half of the reported cases; of those with documented recovery, approximately half received growth factor support. In the remaining cases, information on resolution was not provided. More than half of the reported cases of delayed onset neutropenia occurred in patients who had undergone prior autologous bone marrow transplantation. In an adequately designed, controlled, clinical trial, the reported incidence of NCI-CTC, Grade 3 and Grade 4 neutropenia was

higher in patients receiving RITUXIMAB in combination with fludarabine as compared to those receiving fludarabine alone (76% [39/51] vs. 39% [21/53]).

- **Infectious Events:** Rituxan induced B-cell depletion in 70% to 80% of patients with NHL and was associated with decreased serum immunoglobulins in a minority of patients; the lymphopenia lasted a median of 14 days (range, 1 - 588 days). Infectious events occurred in 31% of patients: 19% of patients had bacterial infections, 10% had viral infections, 1% had fungal infections, and 6% were unknown infections. Serious infectious events (Grade 3 or Grade 4), including sepsis, occurred in 2% of patients.
- **Other Serious Viral Infections:** The following additional serious viral infections, either new, reactivated or exacerbated, have been identified in clinical studies or postmarketing reports. The majority of patients received Rituxan in combination with chemotherapy or as part of a hematopoietic stem cell transplant. These viral infections included JC virus (progressive multifocal leukoencephalopathy [PML]), cytomegalovirus, herpes simplex virus, parvovirus B19, varicella zoster virus, West Nile virus, and hepatitis C. In some cases, the viral infections occurred up to one year following discontinuation of Rituxan and have resulted in death.

Hepatitis B virus (HBV) reactivation with fulminant hepatitis, hepatic failure, and death has been reported in some patients with hematologic malignancies treated with rituximab. The majority of patients received rituximab in combination with chemotherapy. The median time to the diagnosis of hepatitis was approximately 4 months after the initiation of rituximab and approximately one month after the last dose.

PML is a rare and demyelinating disease of the brain caused by infection with the JC virus that usually leads to death or severe disability. JC virus infection resulting in PML and death has been reported rarely in patients with hematologic malignancies receiving rituximab. The majority of these patients had received rituximab in combination with chemotherapy or as part of a hematopoietic stem cell transplant. Cases of PML resulting in death have also been reported in patients with systemic lupus erythematosus (SLE) treated with rituximab. These patients with SLE had longstanding disease, history of prior immunosuppressant therapy, and were diagnosed with PML within 12 months of their last infusion of rituximab.

Physicians should consider PML in any patient presenting with new onset neurologic manifestations. Consultation with a neurologist, brain MRI, and lumbar puncture should be considered as clinically indicated. In patients who develop PML, rituximab should be discontinued and reductions or discontinuation of any concomitant chemotherapy or immunosuppressive therapy should be considered.

- **Bowel Obstruction and Perforation:** Abdominal pain, bowel obstruction and perforation, in some cases leading to death, were observed in patients receiving Rituxan in combination with chemotherapy for DLBCL. In post-marketing reports, which include both patients with low-grade or follicular NHL and DLBCL, the mean time to onset of symptoms was 6 days (range 1 - 77) in patients with documented gastro-

intestinal perforation. Complaints of abdominal pain, especially early in the course of treatment, should prompt a thorough diagnostic evaluation and appropriate treatment.

- **Additional Safety Signals:** The following serious adverse events have been reported to occur in patients following completion of rituximab infusions: arthritis, disorders of blood vessels (vasculitis, serum sickness and lupus-like syndrome), eye disorders (uveitis and optic neuritis), lung disorders including pleuritis and scarring of the lung (bronchiolitis obliterans), that may result in fatal outcomes, and fatal cardiac failure.

